Blue Box Study
Study to Characterize the Effects of Programming Spinal Cord Stimulation (SCS) in
Patients Undergoing a Boston Scientific (BSC) SCS Temporary Trial

CLINICAL INVESTIGATION PLAN

Sponsored By

Boston Scientific Corporation
Neuromodulation
[name]
[name]
United States of America

This protocol contains confidential information for use by the Investigators and their designated representatives participating in this clinical investigation. The protocol should be held confidential and maintained in a secure location.

Do not copy or distribute without written permission from Boston Scientific Corporation.

THESE DOCUMENTS ARE THE PROPERTY OF BOSTON SCIENTIFIC CORPORATION AND SHALL NOT BE REPRODUCED, DISTRIBUTED, DISCLOSED OR USED FOR MANUFACTURE OR SALE OF APPARATUS WITHOUT THE EXPRESS WRITTEN CONSENT OF BOSTON SCIENTIFIC CORPORATION.

Contact Information

Role	Contact
Clinical Contact	[name], M.S. Principal Clinical Research Scientist Boston Scientific Corporation Neuromodulation [name] [name] United States of America [contact] [name]
Coordinating Principal Investigators	Not applicable

Revision History

	Release Date	
	May 18, 2016	
	September 29, 2016	
	June 14, 2019	

2. Protocol Synopsis

Blue Box: Study to Characterize the Effects of Programming SCS in Patients Undergoing a BSC SCS Temporary Trial	
Primary Objective	To characterize the effects of programming patterned SCS pulse trains in patients undergoing a Boston Scientific (BSC) SCS temporary trial.
Test Device	
 All BSC commercially approved Spinal Cord Stimulation SCS trial systems connected to BSC lead(s) [REDACTED]
Study Design	Prospective, multi-center, non-randomized, exploratory, single-arm
[REDACTED]	
[REDACTED]	Up to 3 sites in the US
[REDACTED]	

Blue Box: Study to Characterize the Effects of Programming SCS in Patients Undergoing a BSC SCS Temporary Trial	
	[REDACTED]
Safety Parameters	All device-related and procedure-related adverse events, all serious adverse events and serious adverse device effects will be reported from the time of enrollment until the end of study participation.
Follow-up Schedule	Study assessments will be required, as appropriate, at the following time points: 
 • Screening Visit (up to 14 days prior to Programming Visit) • Programming Visit (Day 0)
Study Duration	Overall study duration is anticipated to take approximately 36 months from first patient enrolled to end of study close out activities.
Key Inclusion Criteria	
[REDACTED] Study candidate is undergoing an SCS trial of BSC neurostimulation system, per local directions for use (DFU).
 
[REDACTED]
 
Subject signed a valid, IRB-approved informed consent form.
 
Subject is 18 years of age or older when written informed consent is obtained.

Key Exclusion Criteria	
[REDACTED] Subject meets any contraindication in BSC neurostimulation system local DFU.
 
[REDACTED]

3. Table of Contents

3.2. Table of Tables

Table 9.2-1: Inclusion Criteria 15

Table 9.3-1: Exclusion Criteria 16

Table 11.1-1: Data Collection Schedule 17

Table 11.6-1: Source Documentation Requirements 20

Table 20.1: Adverse Event Definitions 32

Table 20.3-1: Criteria for Assessing Relationship of Study Device or Procedure to Adverse Event
..... 36

Table 20.4-1: Investigator Reporting Requirements 37

4. Introduction

4.1. *Chronic Pain*

Chronic pain is a significant world-wide complaint and consumes considerable healthcare resources and heavily impacts quality of social and working life for many. A 2001 European investigation showed that 30% of patients treated in primary care facilities were treated by a physician for a pain complaint, and 37% of those patients (11% of total) suffered from chronic pain (Hasselstrom, Liu-Palmgren, & Rasjo-Wraak, 2002). More recently an epidemiological study conducted in Scotland found the prevalence of chronic pain to be 48%, 8% of which is of neuropathic origin. The authors concluded that chronic pain is more prevalent than what previous studies have suggested (Torrance, Smith, Bennett, & Lee, 2006). In a separate European study done in 2006, 19% of adults surveyed reported suffering from chronic pain (Breivik, Collett, Ventafridda, Cohen, & Gallacher, 2006).

In the 2010 report of the health and status of the nation, Health, the U.S. Center for Disease Control and Prevention reports that over 28% of adults suffer from non-fleeting low-back pain. In patients with low-back pain, approximately half of the patients reported limitation in at least one basic action from the following list: movement difficulty, emotional difficulty, sensory difficulty, cognitive difficulty, self-care limitation, social limitation, or work limitation (National Center for Health Statistics, 2011).

Chronic pain can lead to a number of co-morbidities, including reduced health-related quality of life, reduced ability to engage in activities of daily living, increased disability, increased emotional depression, and weight gain due to the adoption of a sedentary lifestyle.

4.2. *Spinal Cord Stimulation*

Spinal cord stimulation (SCS) is a treatment option for chronic pain that has generally been reserved for patients who have failed multiple, and sometimes all, conservative chronic pain therapies. With SCS, an implanted pulse generator (IPG) delivers electrical current to a lead(s) implanted in the epidural space at spinal level(s) where access can be obtained neural structures that are implicated in the chronic pain circuits. Electrically stimulating these nerves creates a comfortable tingling sensation, known as paresthesia, that can be directed to the painful location to mask the sensation of pain (Kumar *et al.*, 2006).

SCS is effective for neuropathic pain associated with a variety of conditions, including failed back surgery syndrome (FBSS), which is the most common condition associated with chronic pain (Carter *et al.*, 2004, Taylor *et al.*, 2004). For best pain relief, the paresthesia must be programmed to overlap the regions of pain (North *et al.*, 1990). To achieve overlap, the electrode contacts are programmed based on the patient's feedback to various combinations of stimulation parameters such as polarities, pulse rate, amplitude, and pulse width.

Two randomized controlled trials (RCTs) have been conducted on the use of SCS to treat patients with FBSS. Each study demonstrated the superiority of SCS compared with the alternative

therapy, reoperation in one case (North *et al.*, 2005) and conventional medical management (CMM), including medication, nerve blocks, physical therapy, massage, etc., in the other (Kumar *et al.*, 2007).

In a single-center study, North *et al.* randomized 50 patients: 24 to SCS and 26 to reoperation. At an average follow-up of 2.9 years, the success rate (at least 50% pain relief and patient satisfaction) was reported to be significantly higher among patients randomized to SCS (9 of 24 patients) than among those randomized to reoperation (3 of 26 patients). Crossover was permitted if a patient's randomized therapy did not provide adequate pain relief, and significantly more patients crossed from reoperation to SCS (14 of 26) than from SCS to reoperation (5 of 24). Six of the reoperation crossovers achieved success with SCS, bringing the success rate to 15 of 38 who received SCS as a final treatment. None of the patients who failed SCS achieved success with reoperation (3 of 31 who received reoperation as a final treatment achieved success).

North *et al.* then used data from this study to compare the cost of SCS versus reoperation over a 2.9-year follow-up period and demonstrated that SCS was the least expensive and was dominant in terms of cost-effectiveness and cost-utility (North *et al.*, 2007).

[figure not shown]
In a separate, international, multi-center RCT, Kumar *et al.* randomized 100 patients: 48 to CMM and 52 to SCS plus CMM (Kumar *et al.*, 2007). At 6 months, patients randomized to SCS achieved significantly greater pain relief and improved functional capacity and health-related quality of life compared with patients randomized to CMM. The patients randomized to SCS who actually received SCS (42 of 52) and were followed for 24 months reported significantly improved leg pain relief, functional capacity, and quality of life compared with their pre-treatment status (Kumar *et al.*, 2008). While initial SCS costs were greater than CMM costs, by 6 months post-randomization, health-related quality of life scores were preferentially improved for the SCS group. Thus, the authors inferred that SCS cost-effectiveness studies must examine costs and quality of life data beyond six months to paint an accurate picture (Manca *et al.*, 2008).

The results of these RCTs provide evidence that SCS is effective and cost effective in relieving chronic neuropathic pain associated with FBSS. North *et al.* also indicate that SCS might provide the best outcome and economic value for patients who are eligible for both SCS and reoperation (North *et al.*, 2007). The results of North's single-center RCT, however, have not been confirmed by a multi-center RCT that reflects the advances in surgical practice and in SCS that might have changed the comparative efficacy of these procedures.

In 2004, FDA approved the Boston Scientific Corporation (BSC) Precision[®] SCS system as an aid in the management of chronic intractable pain of the trunk and/or limbs. The Precision System received CE mark in 2005 for treatment of chronic intractable pain. The results of a multi-center, non-randomized feasibility study conducted with this system demonstrated more than 50% pain relief through a maximum follow-up of 18 months, but the single-arm design and small number of subjects enrolled limit the strength of the conclusions (Oakley *et al.*, 2007).

5. Device Description

5.1. *System Elements*

[figure not shown]
The Blue Box Study SCS System setup is similar to others employed in numerous IRB approved studies where an external electrical stimulator was connected acutely to either SCS or deep brain stimulation (DBS) leads, intraoperatively and during stimulation trials, to deliver acute temporal patterns of stimulation to patients (Tan, et al., 2016; Swan, et al., 2016; Swan, et al., 2015; Tan, et

[figure not shown]
al., 2014; Swan, et al., 2014; Brocker, et al., 2013; Birdno, et al., 2012). The systems used in these studies consist of software on a computer to communicate with an external stimulus generator (via a cable), an isolator to optically isolate the external generator, and a custom interface (passive switch box) to connect the external generator to the lead (via a cable).

5.1.1. Boston Scientific SCS Systems

BSC commercially approved SCS systems are approved by the Food and Drug Administration as an aid in the management of chronic intractable pain of the trunk and/or limbs, including unilateral or bilateral pain associated with the following: failed back surgery syndrome, intractable low back pain and leg pain. These systems include both an External Trial Stimulator (ETS) and an Implantable Pulse Generator (IPG) with their associated components. The ETS are used to perform an initial temporary SCS trial in order to determine a patient's suitability for SCS treatment. If the temporary SCS trial is successful, the IPG is then used for permanent implantation of the SCS system. This study will span the duration of the temporary trial with the use of the ETS and will end upon completion of each subject's study visits, not to exceed 14 days post-Screening Visit. For patients who move forward to a permanent implant, the permanent implant procedure will not be within the scope of this study. Consequently, the IPG and associated components will not be included here.

A Clinician Programmer (CP) is provided to facilitate communication with, and programming of the ETS. A hand-held battery operated remote control provides the patient with the ability to access basic stimulator functions.

[figure not shown]

6. Study Objectives

6.1. Primary Objective

To characterize the effects of programming patterned SCS pulse trains in patients undergoing a Boston Scientific (BSC) SCS temporary trial.

8. Study Design

This is a prospective, on-label, multi-center, non-randomized, exploratory, single-arm study.

[figure not shown]
8.1. Scale and Duration

The study requires a screening visit and a programming visit. Overall study duration

is planned for approximately 36 months from first patient enrolled to completion of end of study close out activities. Figure 8-1 shows the study design

Figure 8-1: Study Design

8.2. Treatment Assignment

Consecutive eligible patients who consent to participation and have met all of the inclusion and none of the exclusion criteria will be enrolled and assigned a unique subject identifier.

8.2.1. Treatment

The study treatment will consist of commercially available neurostimulation program settings with any commercially approved Boston Scientific Precision Spectra neurostimulator for pain.

8.3. Justification for the Study Design

This is a prospective, on-label, multi-center, non-randomized, exploratory, single-arm study. The endpoints of this study are intended to observe the paresthesia paradigms elicited by programming configurations that are within Boston Scientific's currently commercially approved spinal cord stimulation rate, amplitude, and pulse width. The results of this study will also help Boston Scientific guide the development of next generation programming algorithms.

A prospective study design will ensure that identical procedures are followed for data capture and review.

A multi-center design will minimize the impact on the results due to specific surgical placement and intra-operative techniques as well as to minimize bias that may result from differences in patient selection, regional differences in the patient demographic, and patient management.

This study does not require blinding since there is no treatment comparison based on outcomes and all subjects will be undergoing identical procedures. All end-points are exploratory and the design does not require statistical power.

9. Subject Selection

9.1. Study Population and Eligibility

Subjects are established patients in a pain management practice who are eligible to receive an SCS screening trial utilizing a commercially-approved BSC neurostimulation system to treat their pain condition.

9.2. Inclusion Criteria

Subjects who meet all of the following criteria (see Table 9.2-1) may be given consideration for inclusion in this clinical investigation, provided no exclusion criterion (see Section 9.3) is met.

Table 9.2-1: Inclusion Criteria

Clinical Inclusion Criteria	
Study candidate is undergoing an SCS trial of BSC neurostimulation system, per local directions for use (DFU).
 
[REDACTED]
 
Subject signed a valid, IRB-approved informed consent form.
 
Subject is 18 years of age or older when written informed consent is obtained.

------------------------------------	--

Abbreviations: BSC - Boston Scientific Corporation, SCS – Spinal Cord Stimulation, DFU - directions for use, IRB - Institutional Review Board

9.3. Exclusion Criteria

Subjects who meet any one of the following criteria (Table 9.3-1) will be excluded from this clinical study.

Table 9.3-1: Exclusion Criteria

Clinical Exclusion Criteria	Subject meets any contraindication in BSC neurostimulation system local DFU.
------------------------------------	--

Abbreviations: BSC - Boston Scientific Corporation, DFU - Directions For Use, SCS – Spinal Cord Stimulation

10. Subject Accountability

10.1. *Point of Enrollment*

The point of enrollment is the time at which a subject signs and dates the valid, IRB/EC-approved informed consent form. No study-related procedures or assessments can take place until the informed consent form is signed.

10.2. *Withdrawal*

All subjects enrolled in the clinical study (including those withdrawn from the clinical study or lost to follow-up) shall be accounted for and documented. If a subject withdraws from the clinical investigation, the reason(s) shall be reported. If such withdrawal is due to problems related to study device safety or performance, the investigator shall ask for the subject's permission to follow his/her status/condition outside of the clinical study.

Reasons for withdrawal include

- physician discretion,
- subject choice to withdraw consent,
- subject's failure to meet study inclusion or exclusion criteria after enrollment
- lost to follow-up, or
- death

While study withdrawal is discouraged, subjects may withdraw from the study at any time, with or without reason, and without prejudice to further treatment.

All applicable case report forms (CRFs) up to the point of subject withdrawal and an "End of Study" form must be completed. Any subject deemed "lost to follow-up" should have a minimum of three documented attempts to contact him/her prior to completion of the "End of Study" form.

Additional data may no longer be collected after the point at which a subject has been withdrawn from the study or withdraws consent, for whatever reason. All open adverse events should be closed or documented as unresolved. Data collected up to the point of subject withdrawal may be used and analyzed.

10.3. *Subject Status and Classification*

A subject is considered enrolled after a signed informed consent form (ICF) has been obtained. Study participation will end when each enrolled subject completes their study visits, withdraws, or at most 15 days after the Screening Visit if a Programming Visit is not completed.

10.4. *Enrollment Controls*

At the time when the study-wide cap of 35 enrolled subjects is reached, further enrollment into the study will cease. The sponsor will notify all centers when approximately 30 subjects have been enrolled to alert investigators that enrollment will soon cease. The correspondence may also outline the specific activities to minimize the risk of enrollment after the protocol-specified cap of 10 enrolled subjects has been reached.

10.5. *End-of-Study Action Plan*

Subjects will be followed according to standard, routine medical care.

11. Study Methods

11.1. *Data Collection*

The table below illustrates the data that will be collected during the study visit.

Table 11.1-1: Data Collection Schedule

	Screening (≤ 14 Days prior to Day 0)	Programming Visit (Day 0)
Inclusion/Exclusion Criteria Evaluation	X	
Informed Consent (ICF)	X	
Demographics	X	
Medical History	X	
Adverse Events Assessment	X ¹	X
Imaging		X ²
Pain Drawing		X
Pain Intensity		X
Programming		X
Paresthesia Drawing		X ^{3,5}

Stimulation Questionnaire		X ³
Audio Recording		X ⁴

¹ AEs specified in Section 19 must be reported only after signing written informed consent.

² Optional.

³ Complete based on each selected test configuration setting

⁴ Optional Audio recording. Subjects will be asked to have their verbal description of the test configuration sensations recorded on audio. Subjects will be informed that they may refuse permission without penalty.

⁵ Optional Paresthesia Drawing

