11.6. Source Documents

Where copies of the original source document as well as printouts of original electronic source documents are retained, these shall be signed and dated by a member of the study team with a statement that it is a true reproduction of the original source document. All source documentation will be retained at the study site. Examples of source documents include, but are not limited to the following:

Table 11.6-1: Source Documentation Requirements

Requirement	Disposition
Hospital records and/or clinical and office charts including the evidence of but not limited to inclusion/exclusion criteria, informed consent, procedures, laboratory results, medications, assessment of adverse events, health resource utilization information	Retained at study site
Assessments and Questionnaires	Retained at study site and/or retained at sponsor site
Imaging films/prints (if applicable)	Retained at study site
Programming printouts/forms for programming information	Retained at study site
Technical Source Forms	Retained at study site

12. Statistical Considerations

This feasibility study is exploratory in nature and thus no statistical powered end-points are included.

13. Data Management

13.1. *Data Collection, Processing, and Review*

Subject data will be recorded on paper case report forms (CRFs) which will be provided by BSC. The data reported on the CRFs shall be derived from source documents and shall be consistent with these source documents. An exception to this requirement is when data must be recorded directly on the CRF. For example, the questionnaire filled out by the patient describing the details of their pain. Any discrepancies should be explained in writing. Any change or correction made to the clinical data will be dated, initialed and explained, if necessary, and shall not obscure the original entry. A written audit trail shall be maintained which will be made available for review by BSC or its representative.

13.2. *Data Retention*

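### Section 10.4 states two enrollment caps, 35 and 10 subjects, and reading the 10 as a per-site limit does not reconcile them

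*Combined protocol and SAP*

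**What the plan says.** The enrollment limit is set in protocol Section 10.4 (Enrollment Controls), a paragraph of three sentences.

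- The first sets the stopping rule: "At the time when the study-wide cap of 35 enrolled subjects is reached, further enrollment into the study will cease".
- The second sets an early warning: "The sponsor will notify all centers when approximately 30 subjects have been enrolled to alert investigators that enrollment will soon cease".
- The third says what that correspondence may also cover, namely activities to "minimize the risk of enrollment after the protocol-specified cap of 10 enrolled subjects has been reached".

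The synopsis gives the number of centers as "Up to 3 sites in the US". Section 12 (Statistical Considerations) offers no sample-size derivation: "This feasibility study is exploratory in nature and thus no statistical powered end-points are included".

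The counted unit is defined twice in the same sense. Section 10.1 says "The point of enrollment is the time at which a subject signs and dates the valid, IRB/EC-approved informed consent form", and Section 10.3 says "A subject is considered enrolled after a signed informed consent form (ICF) has been obtained". Section 8.2 is worded a little differently: "Consecutive eligible patients who consent to participation and have met all of the inclusion and none of the exclusion criteria will be enrolled".

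**The concern.** The first and third sentences of Section 10.4 both name a cap on enrolled subjects, and they give different numbers. This is current operative text, not a change log, and both figures are fully legible.

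The cap is the only legible limit on how many people are enrolled and may be exposed to the study system. A site, monitor or IRB reading the paragraph meets two limits. Section 15 requires every deviation to be logged and reported to the sponsor, and Section 23.4 lets the sponsor stop inclusion at a center for multiple or severe violations. Someone who takes the 10 literally could record the eleventh subject onward as deviations that did not occur. The sentence with the 10 also describes the letter meant to prevent over-enrollment, so the wrong figure could be copied into that letter.

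**Working it through.** **Inputs**

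| Quantity | Value | Source |
|---|---|---|
| Study-wide cap | 35 enrolled | Section 10.4, first sentence |
| Alert to centers | about 30 enrolled | Section 10.4, second sentence |
| Protocol-specified cap | 10 enrolled | Section 10.4, third sentence |
| Sites | at most 3 | Section 2, synopsis |
| Unit counted | signed consent | Sections 10.1 and 10.3 |

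No power or precision calculation is given, so neither cap can be reproduced from one. The check is whether any reading lets 35, 30 and 10 stand together.

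**Reading 1: 10 is study-wide.** This contradicts 35 directly. The warning that enrollment is about to end would go out 30 − 10 = 20 subjects after the cap, at 30/10 = 3 times the limit. Under a cap of 35 the same warning leaves 35 − 30 = 5 places, which is what a warning is for.

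**Reading 2: 10 is per site.** Maximum enrollment is the number of sites × 10:

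- 1 site: 10
- 2 sites: 20
- 3 sites: 30

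The largest value is 35 − 30 = 5 short of the study-wide cap. Reaching 35 at 10 per site needs 35/10 = 3.5, so at least 4 sites, and the synopsis allows 3. With 3 sites, 35 means an average of 35/3 = 11.7, so at least one site must enroll 12 or more. The alert at about 30 would go out when every site was already full.

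**Reading 3: the two caps count different things.** Both sentences refer to enrolled subjects, and Sections 10.1 and 10.3 define enrollment as signed consent. There is only one unit.

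**Size of the gap**

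- Enrollment ratio: 35/10 = 3.5.
- Standard-error ratio for a subject-level mean or proportion: √3.5 = 1.87.
- 95% half-width for a proportion of 50%, 1.96 × √(0.25/n): 0.166 at n = 35 and 0.310 at n = 10, or about 17 and 31 percentage points.
- One-sided 95% upper limit on an event rate with zero events observed, 1 − 0.05^(1/n): 0.082 at n = 35 and 0.259 at n = 10, or 8.2% and 25.9%.

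The precision figures take every enrolled subject as contributing and treat the subject as the unit. In practice some subjects who consent may not be tested, and one subject may contribute several test configurations. The plan sets no precision target, so these figures only illustrate the distance between the two caps.

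**The case against.** The strongest reply is that this is an editorial slip. Only the first sentence of Section 10.4 sets a rule, and the alert at about 30 fits only that rule. The sentence with the 10 is permissive: it describes what a letter may contain. No procedure, endpoint or analysis depends on it, and a site would have to overlook the explicit stop at 35 to act on 10. Most of this stands. It is why an actual stop at 10 is unlikely and why the consequence is limited to confusion and possible false deviations.

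A second reply is that a site limit of 10 can logically sit beside a study limit of 35, since both are upper bounds. That is true, but with at most 3 sites it makes 35 unreachable and the alert pointless, and the text has no per-site wording. Synopsis rows next to the site count are redacted and may hold a subject number or a site limit. That could show which number was meant, but it would not remove the conflict printed in Section 10.4.

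A third reply is that the precision figures compare 35 with a sample size nobody expects, and that the cap counts consents rather than subjects tested: Section 10.2 allows withdrawal for failing criteria after enrollment, and Section 11.5 allows for a missed Programming Visit. This is fair. The figures carry no weight in the conclusion.

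The difference in Section 8.2 is also minor. Sections 10.1 and 10.3 define enrollment expressly, and the counting unit is not in real doubt.

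**Conclusion.** The concern holds. Section 10.4 gives two numbers for the same limit, 35 and 10, a 3.5-fold difference, and no reading of the legible text reconciles them. The internal evidence favors 35, and the 10 is most likely an uncorrected figure, although the documents do not confirm this. There is no loss of power, because nothing is powered.

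The conclusion rests on two assumptions: that the visible limit of 3 sites is not altered by a redacted row, and that enrolled means signed consent in both sentences, as Sections 10.1 and 10.3 define it. The point should be fixed because it concerns the only legible enrollment limit and costs almost nothing to correct.

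**What to change.** The sponsor should confirm which cap is intended and state that one number in both sentences of Section 10.4. If it is 35, change the 10 in the third sentence to 35, and check any subject number in the redacted parts of the protocol against it. Keep signed consent (Sections 10.1 and 10.3) as the counted unit. As a minor edit, align the wording of Section 8.2 with that definition.

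The cost is one corrected number with the usual IRB notice. If 35 is intended, neither the cap nor the counting unit changes, so no patients or procedures are added.
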